15. Has known hypersensitivity to any of the components of tazemetostat or other inhibitor(s) of EZH2, or hypersensitivity to Ora-sweet or methylparaben.

**Dosage and
Administration for
Tazemetostat:**

16. Has an uncontrolled intercurrent illness including, but not limited to, uncontrolled infection, or psychiatric illness/social situations that would limit compliance with study requirements.

17. **For female subjects of childbearing potential:** Is pregnant or nursing

For male subjects: Is unwilling to adhere to contraception criteria from time of enrollment in study to at least 3 months after last dose of tazemetostat.

Oral Suspension: Subjects will receive tazemetostat as an oral agent BID.

The starting dose for the dose escalation will be 240 mg/m²/dose given BID for a total daily dose of 480 mg/m²/day. Dose escalation will be performed using a “Rolling 6” design. The starting dose is derived from physiologically based PK modeling of observed PK data in adult subjects.

Dose Expansion: For patients with no CNS involvement, the dose will be 520 mg/m² given BID. For ATRT and tumors with CNS involvement the dose will be 1200 mg/m² given BID.

Tablet Formulation: Subjects in Cohort 4 will receive orally administered tazemetostat tablets 800 mg/m² TID (2400 mg/m²/day) CCI

Treatment may continue, assuming subject and/or parent/guardian and Investigator consent, until disease progression or unacceptable toxicity. Tazemetostat will be administered for a maximum of 2 years.

Criteria for Evaluation:

Primary Endpoints:

Dose Escalation:

- Incidence and severity of treatment-emergent AEs (TEAEs) qualifying as protocol-defined DLTs, and establishment of the protocol-defined RP2D and/or MTD.

Dose Expansion:

- Overall response rate (CR + PR) to tazemetostat in pediatric subjects with relapsed or refractory ATRT (Cohort 1), non-ATRTR rhabdoid tumors (Cohort 2), INI1-negative tumors (Cohort 3), and tumor types eligible for Cohorts 1 through 3 or synovial sarcoma with SS18-SSX rearrangement (Cohort 4) using disease-appropriate standardized response criteria.

Secondary Endpoints:

Dose Escalation:

- Overall response rate (CR+PR) to tazemetostat in pediatric subjects with relapsed or refractory CNS and solid tumors, using disease-appropriate standardized response criteria

Dose Expansion:

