	15	5	2380 (52.0)	2 (2 – 4)	9810 (33.3)	21,000 (32.6)
1200	1	6	1950 (61.4)	2 (2 – 8)	6640 (85.2)	NC
	15	6	3860 (31.6)	2 (1 – 2)	13,900 (38.2)	29,700 (43.9)

Abbreviations: BID= twice daily, C_{max}= maximum plasma concentration, T_{max}= Time to maximum concentration, AUC=Area under the concentration-time curve.

^aMedian (range) T_{max}

^bLast PK blood sample collection time point = 8 h

^cAUC₍₀₋₂₄₎ on Day 15 calculated as AUC₍₀₋₁₂₎ × 2

NC = not calculated

In children 1 to 18 years of age, the mean AUC₍₀₋₂₄₎ and C_{max} on Day 15 did not increase in a dose-proportional fashion at each dose level. There was an apparent trend for mean AUC₍₀₋₂₄₎ and C_{max} on Day 15 to increase in a greater than dose-proportional fashion when the tazemetostat dose increased from 240 mg/m² BID to 1200 mg/m² BID. The mean AUC₍₀₋₂₄₎ after administration of tazemetostat 1200 mg/m² BID is greater than the AUC₍₀₋₂₄₎ observed from the 50 mg/kg day dose group in which thymic lymphoma was observed in a single female rat in the 18-week toxicity study conducted in juvenile rats (18,500 ng•h/mL). However, the mean AUC₍₀₋₂₄₎ after administration of tazemetostat 1200 mg/m² BID is approximately 4-fold less than the AUC₍₀₋₂₄₎ from male rats in the 150/300 mg/kg day dose group (125,000 ng•h/mL) in which the incidence of thymic lymphoma appeared to increase to 4 of 21 animals in the 18-week toxicity study conducted in juvenile rats. (For more information on the results from the 13-week see Section 1.6.1.)

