- d. INR is the preferred value to be measured but if only PT can be performed in the testing laboratory that is acceptable
- e. Creatinine clearance by 24-hour urine or radioisotope glomerular filtration rate
- f. Eligibility can be determined by either total or conjugated bilirubin
- g. If attributed to tumor involvement, AST and ALT <5xULN

NOTE: Laboratory results obtained during Screening should be used to determine eligibility criteria. In situations where laboratory results are outside the permitted range, the Investigator may retest the subject and the subsequent within range Screening result may be used to determine the subject's eligibility.

11. For subjects with CNS involvement: Subjects must have:

- Deficits that are stable for a minimum of 14 days prior to first dose of study drug, or
- Seizures that are stable, not increasing in frequency or severity and controlled on current anti-seizure medication(s) for a minimum of 7 days prior to first dose of study drug, or
- Treated brain metastases without evidence of progression (new or enlarging brain metastases by imaging 4 weeks prior to the first dose of study drug), and are on stable or tapering doses of steroids for at least 7 days prior to first dose of study drug.

NOTE: Subjects with leptomeningeal disease or brain tumors with positive cerebral spinal fluid cytology are eligible for this study. Subjects may receive glucocorticoids (at stable or tapering dose) to control CNS symptoms prior to enrollment; however, subjects should receive a stable or tapering dose for at least 7 days prior to first dose of study drug.

12. Has a left ventricular (LV) fractional shortening of >27% or an LV ejection fraction of ≥50% by echocardiogram (ECHO) or multigated acquisition scan (MUGA) and New York Heart Association Class ≤2.
13. Has a QT interval corrected by Fridericia's formula (QTcF) ≤450 msec
14. Is able to swallow and retain orally administered medication and does not have any uncontrolled gastrointestinal (GI) condition such as nausea, vomiting or diarrhea, or any

clinically significant GI abnormalities that may alter absorption such as malabsorption syndromes, hereditary fructose intolerance, glucose-galactose malabsorption, sucrose-isomaltase insufficiency, or major resection of the stomach and/or bowels.

NOTE: Nasogastric and gastrostomy tube administration of the oral suspension formulation of study drug is permitted.

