14. **For subjects with CNS involvement (primary tumor or metastatic disease):** Have any active bleeding, or new intratumoral hemorrhage of more than punctate size on Screening MRI obtained within 14 days of starting study drug, or known bleeding diathesis or treatment with anti-platelet or anti-thrombotic agents.
15. Has known hypersensitivity to any of the components of tazemetostat or other inhibitor(s) of EZH2, or hypersensitivity to Ora-sweet or methylparaben.
16. Has an uncontrolled intercurrent illness including, but not limited to, uncontrolled infection, or psychiatric illness/social situations that would limit compliance with study requirements.
17. **For female subjects of childbearing potential:** Is pregnant or nursing
For male subjects: Is unwilling to adhere to contraception criteria from time of enrollment in study to at least 3 months after last dose of tazemetostat.

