5.3 Dosage and Administration

Tazemetostat must be dispensed or administered only to subjects enrolled in the study and in accordance with the protocol. Standard institutional procedures for administering an oral agent via by mouth will be followed. An adequate supply will be provided with instructions on home administration.

Tazemetostat administered to newly enrolled subjects: Based on benefit-risk assessment of the population studied in this clinical trial, following a report of CCI in a pediatric patient, from the time Amendment 7.0 approval to the completion of enrollment, the following doses will be the starting dose for new enrolled patients: For new patients with ATRT or any INI1-negative tumors with CNS involvement, the starting dose will remain 1200 mg/m² BID. For new patients that are non-ATRT, the starting dose will be 520 mg/m² BID. (See Section 6.5.3).

Tazemetostat administered as an oral suspension: The starting dose of tazemetostat (for dose escalation only) will be 240 mg/m²/dose given BID (based on free base) = 480 mg/m²/day. The amount of suspension per dose is calculated based on the subject's body surface area (BSA) and the assigned dose level. After the completion of Cycle 1, if a subject is unable to continue dosing with the oral suspension formulation due to adherence issues, the Medical Monitor should be contacted to discuss the possibility of switching to tablet dosing options.

Tazemetostat administered as a tablet (subjects in Cohort 4 only; Cohort 4 is closed to enrollment): Tazemetostat will be orally administered at the dose of 800 mg/m² TID (2400 mg/m²/day). Please see CCI for tablet dosing nomogram. This will provide instruction on the number of tablets to be taken based on BSA. After the completion of Cycle 1, if a subject is unable to continue dosing TID with the tablet formulation because of the quantity of tablets or schedule, the Medical Monitor should be contacted to discuss the possibility of switching to BID tablet dosing or BID suspension dosing.

For subjects on the tazemetostat BID oral suspension schedule, doses should be administered as close to 12 hours apart as possible, but there should be no less than 8 hours between doses. For subjects on the TID tablet schedule, doses should be administered as close to 8 hours apart as possible, but there should be no less than 4 hours between doses. Doses may be taken with or without food.

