6.5.3 Dose Modification due to Risk of Adverse Events of Special Interest

6.5.3.1 Dose Modification After Complete or Partial Response

For all responding patients (with CR or PR), regardless of indication, the dose will be either reduced to 520 mg/m² BID, or stopped at one year from the first observed response based on the treating Investigator’s decision. Patients will remain on study, and upon disease progression, may be rechallenged with treatment at a dose of 520 mg/m² BID for non ATRT patients, or at dose 1200 mg/m² BID for patients with ATRT or any INI1-negative tumors with CNS involvement. Overall treatment should not exceed 2 years of cumulative dosing (Figure 3).

Figure 3 Dose Modification Schematic for Patients With Complete or Partial Response

[figure not shown]

Abbreviations: ATRT= atypical teratoid tumor, CNS= central nervous system, CR= complete response, INI1= Integrase interactor 1, PD= progressive disease.

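### The starting-dose rule does not define mutually exclusive groups and differs between Section 5.3, the synopsis and the SAP for non-ATRT subjects with CNS involvement

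*Protocol*

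**What the plan says.** **Protocol Section 5.3** sets the dose for newly enrolled subjects in two consecutive sentences. The first reads "For new patients with ATRT or any INI1-negative tumors with CNS involvement, the starting dose will remain 1200" mg/m² BID. The second reads "For new patients that are non-ATRT, the starting dose will be 520" mg/m² BID. Section 1.5.2.2 repeats the pair. Sections 3.3, 6.4 and 6.5 send the reader to Section 5.3 for new-patient dosing.

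**The synopsis** (Dosage and Administration) divides expansion subjects on a different variable: "For patients with no CNS involvement, the dose will be 520" mg/m² BID, and "For ATRT and tumors with CNS involvement the dose will be 1200" mg/m² BID. It has no INI1 condition, and its 520 group is defined by absence of CNS involvement rather than by histology.

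**The rechallenge rules** in Sections 6.5.3.1 and 6.5.3.2 follow the pattern of Section 5.3. Section 6.5.3.1 gives 520 mg/m² BID "for non ATRT patients, or at dose 1200" mg/m² BID for ATRT or an INI1-negative tumor involving the CNS.

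**SAP Section 3.1** says that Cohorts 1 to 3 receive 1200 mg/m² BID and mentions no 520 group.

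**The concern.** Cohorts 1 and 4 are closed, so new expansion subjects enter Cohorts 2 and 3, which are non-ATRT. Read literally, the 520 sentence covers all of them. The 1200 sentence can now act only through its CNS clause, and that is where the two sentences meet.

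The starting dose also fixes later management. Under Section 6.5, a subject who starts at 1200 mg/m² BID has the reduction steps of Table 6. A subject who starts at 520 mg/m² BID has no permitted modification, only interruption for up to 14 days and then discontinuation if the event has not resolved. In the SAP, dose feeds the response rate by dose level (Section 15.1) and the assigned-dose denominator of compliance (Section 14.2). Section 5.3 introduced the split as a benefit-risk measure after a report in a pediatric patient, so the assignment should be unambiguous.

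**Working it through.** There is no sample size, power or error rate to reproduce. The check has three parts: whether the subjects can be enrolled, what each text assigns them, and how far apart the assignments are.

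**1. Eligibility.** Inclusion criterion 11 (Section 4.2) admits subjects with "Treated brain metastases without evidence of progression", and its note admits leptomeningeal disease. Exclusion criterion 14 (Section 4.3) opens with "For subjects with CNS involvement (primary tumor or metastatic disease", so CNS involvement is not confined to primary CNS tumors. Section 4.2.2 accepts loss of either INI1 or SMARCA4 for MRT and RTK, so a Cohort 2 tumor need not be INI1-negative. Its INI1-negative criterion, which governs Cohort 3, requires INI1 loss.

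**2. Assignment.** Each text is applied to each type of subject (mg/m² BID). The exception reading treats the first sentence of Section 5.3 as carved out of the second.

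| Subject | Section 5.3, literal | Section 5.3, exception reading | Synopsis | SAP 3.1 (Cohorts 1–3) |
|---|---|---|---|---|
| ATRT | 1200 | 1200 | 1200 | 1200 |
| Non-ATRT, no CNS involvement | 520 | 520 | 520 | 1200 |
| Non-ATRT, INI1-negative, CNS involvement | 520 and 1200 | 1200 | 1200 | 1200 |
| Non-ATRT, SMARCA4 loss with INI1 retained, CNS involvement | 520 | 520 | 1200 | 1200 |

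In the third row the literal text gives two answers, but the exception reading and the synopsis agree. In the fourth row Section 5.3 gives one answer on either reading and the synopsis gives the other. The SAP column departs from both protocol texts in the second row.

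The text of Sections 6.5.3.1 and 6.5.3.2 has the same overlap as Section 5.3 and does not say when CNS involvement is determined. Figures 3 and 4, which illustrate those rules, were not available for this review.

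**3. Size of the difference.**
- Dose: 1200 / 520 = 2.31.
- Exposure (Table 2, Day 15 geometric mean AUC(0–24)): 29,700 / 12,500 = 2.38. These values are preliminary, with n = 6 at each dose and CVs of 43.9% and 35.1%. The table is not monotone: 700 mg/m² BID gives 8,140 ng•h/mL, below the 12,500 at 520. The dose ratio is exact; the exposure ratio is only indicative.
- Weight in a cohort: the number of affected subjects is not given. Each one is 1/20 = 5% of a full cohort of 20.

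**The case against.** The strongest reply is that Section 5.3 should be read as a whole. ATRT is already named in its first sentence. If the second sentence took in every non-ATRT subject, the added CNS clause would have no work to do. A named exception followed by the remainder is the natural construction, and the synopsis agrees with it for INI1-negative tumors. This stands as a reading of the text. A reader might infer that the dose of every non-ATRT subject with CNS involvement is indeterminate; the documents do not support that. The reply does not reach the SMARCA4 case, where the exception reading still leaves Section 5.3 and the synopsis apart.

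The remaining group is narrow. The protocol treats ATRT as the CNS form of rhabdoid tumor and refers to MRT and RTK as non-CNS tumors. Section 1.1 reports INI1 loss in up to 98% of childhood rhabdoid tumors, and Cohort 3 requires INI1 loss. Appendix 4 classes leptomeningeal disease as non-measurable, so a subject with that alone would not meet the expansion requirement for measurable disease. All of this argues for small numbers, not for consistent wording.

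Section 15.5 directs sites to the Medical Monitor for clarification, and the Pharmacy Manual was not available. It therefore cannot be claimed that sites are in fact dosing alike subjects differently. The case of a first CNS lesion at the progression that triggers rechallenge is hypothetical, and the figures may address it.

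A reader might also note that 18,500 ng•h/mL, the juvenile-rat exposure in the dose group "in which thymic lymphoma was observed in a single female rat", lies between the two Table 2 means, and treat it as a safety threshold. One animal and two preliminary means do not establish a threshold, and the point does not rely on it.

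**Conclusion.** The concern holds as a defect of wording in a dose-assignment rule, in three parts of unequal weight:

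- **Direct conflict:** a non-ATRT Cohort 2 subject with SMARCA4 loss, retained INI1 and CNS involvement is assigned 520 mg/m² BID by Section 5.3 and 1200 mg/m² BID by the synopsis.
- **Literal overlap with inferable intent:** a non-ATRT, INI1-negative subject with CNS involvement meets both sentences of Section 5.3. The overlap recurs in the rechallenge text.
- **Third version:** SAP Section 3.1 applies 1200 mg/m² BID to all of Cohorts 1 to 3.

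The doses differ 2.31-fold, and the starting dose changes which modification rules apply. The number affected is not stated and is probably small, so no effect on a cohort's response rate can be calculated. The conclusion rests on the text of the sections named and on the eligibility criteria that admit these subjects. It takes no view on which dose is right. The wording should be corrected because Section 5.3 is the section that other parts of the protocol cite for new-patient dosing.

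**What to change.** Reconcile the synopsis, Sections 1.5.2.2, 5.3, 6.5.3.1 and 6.5.3.2 of the protocol, and SAP Section 3.1 to one assignment rule. That rule should:

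- use the same variables everywhere and define groups that do not overlap;
- place every non-ATRT subject with CNS involvement, both INI1-negative and SMARCA4-negative, in one stated group;
- state when CNS involvement is determined, for the starting dose and for rechallenge.

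Figures 3 and 4 should be checked against the result. The dose for each group and the time of determination are for the sponsor to decide; neither is proposed here. The cost is wording in five places in the protocol and one in the SAP, by amendment or clarification. No procedure, visit or sample-size change follows.

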5.4 Procurement of IP

The initial shipment of tazemetostat to a clinical site will occur after all essential regulatory documents (including, but not limited to the receipt of the signed protocol signature page, signed

Form FDA 1572, curriculum vitae of principal Investigator and designees, IRB/ EC approval letter, and approved informed consent form [ICF]) are collected. Refer to the Pharmacy Manual for directions on re-supply shipments.

5.5 Accountability

The Investigator/designee will be responsible for taking an inventory of each shipment of tazemetostat received and comparing it with the accompanying shipment form. The Investigator/designee will verify the accuracy of the information on the form, sign and date it, and acknowledge the shipment receipt according to the instructions provided.

The Investigator/designee must keep accurate written records of all tazemetostat received from the Sponsor. Additionally, the Investigator/designee must keep accurate records of the tazemetostat dispensed to subjects enrolled in this study including the quantity of suspension/number of tablets, lot number, date dispensed, subject initials and identification number, dose administered, balance forward, and the initials of the person dispensing the IP. Based on the entries in the site accountability forms, it must be possible to reconcile IP delivered with that used and returned. All IP must be accounted for and all discrepancies investigated and documented appropriately.

Tazemetostat stock may not be removed from the investigative site where originally shipped without prior knowledge and consent of the Sponsor or its designee. When authorized, all applicable local, state, and national laws must be adhered to for the transfer.

At the end of the study, all unused tazemetostat will be destroyed by the investigative site or sent to a designated contractor for disposal on behalf of the Sponsor, per the instructions at that time. Any IP returned to the Sponsor-designated contractors must be counted and verified by site personnel and the Sponsor or its designee. All certificates of delivery/receipts and/or return forms must be signed prior to shipment. The IP for return must be packed in a tamper-evident manner to ensure integrity is maintained during return. All IP returned must be in accordance with local, state, and national laws and must first be authorized by the Sponsor prior to shipment.

6 STUDY TREATMENT

6.1 Treatment Assignment

Subjects will be identified by a unique subject number that will remain consistent for the duration of the study.

6.2 Restrictions During Study Treatment

Subjects will abstain from ingesting Seville oranges and grapefruit or grapefruit juice and foods/beverages that contain those, for 24 hours prior to the first dose of study treatment until the last dose of study treatment.

Subjects should avoid prolonged exposure to sunlight while receiving study treatment. In addition, subjects should take other measures to avoid UV exposure such as wearing sun screen and sun glasses, wearing protective clothing, and avoiding tanning beds.

6.3 Dose-Limiting Toxicity (DLT)

A DLT will be determined in the first treatment cycle only (Day 1 to Day 28) of dose escalation and will be graded according to the CTCAE version 4.03. A DLT will be defined as a significant adverse reaction (with the exception of tumor progression) that occurred any time from the initial dose of study treatment through the end of the first cycle of treatment in dose escalation that meets any of the following criteria:

- **Non-hematologic toxicity:** any other Grade 3 or greater **non-hematologic** toxicity except:
 - alopecia
 - fatigue/asthenia
 - transient myalgia/arthralgia
 - Grade 3 vomiting or diarrhea that resolves to \leq Grade 2 within 48 hours (with or without supportive care)
 - Grade 3 nausea that resolves (with or without supportive care) to \leq Grade 2 within 7 days
 - Grade 3 anorexia requiring enteral or parenteral nutrition
- **Hematologic toxicity:** myelosuppression, defined as:
 - Grade 4 thrombocytopenia of any duration (by CTCAE, version 4.03) or Grade 3 thrombocytopenia with bleeding or lasting >7 days
 - Grade 4 neutropenia for five consecutive days (by CTCAE, version 4.03)
- Treatment delay of more than 14 days due to delayed recovery from a toxicity related to treatment with tazemetostat

6.4 Maximum Tolerated Dose (MTD), and Recommended Phase 2 Dose (RP2D)

The MTD and RP2D are defined as the dose level below which >1 subject of 3 or ≥ 2 subjects of 6 experience a DLT on the dose-escalation portion of the study during Cycle 1. In the event that MTD is not reached, the RP2D will be that dose that results in a mean $AUC_{(0-24)}$ of at least 5900 ng•h/mL (~80% of the mean value observed after administration of 800 mg BID in adults) or provides biologic and/or clinical activity in subjects in this study. For new patient dosing levels, refer to Section 5.3.

6.5 Dose Modification

During dose escalation, dose modifications are not allowed during Cycle 1. Any AE that is severe enough (at the discretion of the Investigator and with permission of the Sponsor/Medical Monitor) to warrant a dose reduction during Cycle 1 will be discussed with the Medical Monitor prior to resumption of study treatment.

Subjects who have an interruption in treatment for >14 days may restart treatment with tazemetostat after consultation with the Medical Monitor.

For any case of CCI /T-ALL, MDS/AML, or other myeloid malignancies like MPN, tazemetostat will be discontinued and the patient will be followed until resolution of the event.

No dose modification is required for the following Grade 3 or greater non-hematologic toxicities:

- Transient fatigue or asthenia
- Transient myalgia or arthralgia
- Nausea that resolves to <Grade 2 within 7 days (with or without anti-emetics)
- Vomiting that resolves to <Grade 2 within 48 hours (with or without anti-emetics)
- Diarrhea that resolves to <Grade 2 within 48 hours

For subjects in the dose-escalation portion of the study, refer to Table 4 for a description of dose levels to be used for dose modification. For example, a dose reduction of one dose level for a subject on a dose of 1200 mg/m² BID would be 900 mg/m² BID and that for a subject at a dose of 900 mg/m² BID would be 700 mg/m² BID.

For subjects on the dose expansion portion of the study, refer to Section 5.3 for new patient dosing levels.

- For subjects starting at 1200 mg/m² BID, refer to Table 6, below, for a description of dose level modifications.
- For subjects on the tablet formulation (Cohort 4), refer to CCI for instructions on how to administer tablets for each dose level.

Table 6. Dose Modification/Dose Reduction for Dose Expansion Portion

Starting Dose	1200 mg/m ² BID - OR - discontinue
Dose Level - 1	900 mg/m ² BID - OR - discontinue
Dose Level - 2	700 mg/m ² BID - OR - discontinue
Dose Level - 3	520 mg/m ² BID - OR - discontinue

- For subjects starting at the 520 mg/m² BID dose level in the dose expansion portion, no dose modifications are permitted. For these subjects, dosing may be interrupted for up to 14 days to allow resolution of AEs, and subjects must be discontinued if the AE does not resolve with dose interruption.

